#### **Final Visit Day 15 (8 AM $\pm$ 2 days)**

- Review Progress Notes and the medication record to collect information for any adverse events or new concomitant medications since Day 7 (from EHR if subject still hospitalized, otherwise by phone or other digital media).
- Collect results for SOC hematology/chemistry from the EHR if subject still hospitalized.
- Collect inflammatory markers from EHR for those analyzed locally; collect samples for DHO and cytokine panel to be analyzed at the central laboratory if subject still hospitalized.
- Collect NEWS2 Assessments from the EHR.
- Collect nasopharyngeal viral load sample.
- Collect hospital status (hospitalized, hospitalized in ICU, discharged).

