--	--

	
changed concomitant medications since Day 7 (collect from EHR if subject still hospitalized, otherwise by phone or other digital media).
 

• Collect SOC hematology/chemistry results from EHR if subject still hospitalized.

• Collect results for inflammatory markers from EHR for those analyzed locally; collect and process samples for DHO and cytokine panel to be analyzed at the central laboratory on.

• Collect and process nasopharyngeal viral load samples.

• Record hospitalization status (hospitalized, hospitalized in ICU, discharged).

• Collect NEWS2 Assessments from EHR.

• If the subject is being discharged prior to Day 15, follow procedures below.

 
Day 29 (8 AM ± 3 Days)
 

• Determine survival status from EHR if available or by telephone/digital media per institutional guidelines.

 
Hospital Discharge Before Day 15
 
Subjects discharged from the hospital prior to the Day 15 visit are to return to a research facility when feasible for the remaining study visits. All scheduled study assessments are to be completed at these visits when conducted at a research facility.
 
For subjects in the brequinar treatment group discharged from the hospital prior to Day 5, the subject is to take home the remaining doses of brequinar for daily self-administration. All subjects (brequinar and SOC) should have the scheduled assessments, e.g. lab samples and the nasopharyngeal swab, on the day of discharge and enter these results on the appropriate EDC page. Following discharge, subjects are to return to the research or out-patient lab collection facility for the remaining study visits, if feasible. Out-patient lab results are to be entered into the EDC and reviewed by a member of the study team. It is important that every effort be made to have subjects return at least on Days 7 and 15, if feasible. Subjects in the brequinar group are to record brequinar dosing on the medication diary provided by the study team. The study team will arrange for the subject to return any unused study medication to the research facility.
 
For all subjects, if discharge occurs on Days 10, 11, or 12, ensure a hematology/chemistry sample has been obtained on the day of discharge and record these results on the appropriate EDC page. Following discharge, the subject is to return to the research or out-patient lab collection facility for the Day 15 visit if feasible. Out-patient lab results are to be entered into the EDC and reviewed by a member of the study team.
 
If discharge occurs on Days 13, 14 or 15, complete the Day 15 Final Visit activities prior to discharge. No further visits are required unless follow up is needed for a

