### Days 1 - 7 (8 AM ± 8 hours)

- If Day 1 is a different date from Screening, confirm subject continues to meet all inclusion and no exclusion criteria.
- Randomize the subject (record date and time of randomization).
- Review Progress Notes and medication records to collect any new or changes to ongoing adverse events or new or changed concomitant medications since previous visit (may be omitted on Day 1 if Screening visit was conducted on same day as Study Day 1). Repeat daily until discharge.
- Collect SOC hematology/chemistry results from the EHR beginning on Day 1 (pre-dose) (may be omitted for Day 1 if Screening visit conducted on same date as Study Day 1) then daily through Day 7 or until the clinician decides daily testing is no longer necessary. Ensure that Day 1 samples are obtained prior to first dose of study drug, if applicable.
- Days 1 (pre-dose), 3, 5, 7:
  - Collect NEWS2 Assessments from the EHR.
  - Collect results for inflammatory markers from EHR for those analyzed locally; collect, process and ship samples for DHO/brequinar PK and cytokine panel to be analyzed at the central laboratory per the Laboratory Manual.
  - Collect and process SARS-CoV-2 nasopharyngeal viral load samples.
  - Record hospitalization status (hospitalized, hospitalized in ICU, discharged) (Day 1 already recorded as part of Inclusion criteria, do not record again).
- Dispense study medication (Days 1 through 5 if in brequinar group) and record date and time of brequinar administration. Keep the drug administration interval as close as possible

PROTOCOL NUMBER: CCB-CRISIS-01  
PROTOCOL VERSION FINAL DATE: 10SEPT2020

Page 37 of 58

to 24 hours. Ensure Day 1 labs are drawn prior to first brequinar dose on Day 1. If a subject taking brequinar is discharged prior to Day 5, give the subject adequate study drug to take home along with a diary to record daily treatment administration through Day 5.

- Drug accountability Day 7  $\pm$  2 days.

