### **9.6 Compliance with Study Procedures**

The time at which study procedures are conducted should follow the protocol timelines as closely as possible. However, it is recognized in a clinical setting that protocol-specified timings may not occur exactly as specified in the protocol. Provided that activities are carried out within the identified windows it will not be necessary to file a protocol deviation. It is understood that some scheduled study assessments may not be able to be conducted if the subject is unable to return to the clinic after discharge due to COVID-19 restricted travel; it is also understood that crowded hospital conditions/lack of personnel may make it impossible to carry out all requested study procedures; this will not be counted as a protocol deviation. The Day 7 and 15 visits are to be conducted via telephone if the subject has been discharged from the hospital with lab draws for subjects in the brequinar treatment group as described in [Section 8.5](#).

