## 10 ADVERSE EVENT REPORTING

An adverse event is any untoward medical occurrence in a patient or clinical trial subject administered a medicinal product and which does not necessarily have a causal relationship with this treatment. An AE can therefore be any unfavorable and unintended sign (including an abnormal laboratory finding), symptom, or disease temporally associated with the use of the medicinal product, **whether or not considered related to the medicinal product.**

Events that occur prior to informed consent will be entered as medical history; AEs that occur after informed consent will be entered on the AE form.

Subjects will be questioned and observed for evidence of AEs, whether or not judged by the Investigator or designated person to be related to study drug. All AEs will be documented in the subject's medical record and CRF. For any pre-existing condition or abnormal laboratory finding that changes in severity after dosing, this change should be recorded as an AE. New abnormal laboratory findings that are clinically significant are considered AEs.

All adverse events will be collected from the time of informed consent through Day 15. After Day 15, collect/record only Serious Adverse Events (SAEs) or those judged by the Investigator or designated person to be related to study drug. AE details are to be documented including start and stop date and times, whether continuous or intermittent, severity, any intervention utilized to correct the event (e.g., medication, surgery, or other therapy), outcome and the relationship to the study drug.

AEs identified in the protocol as critical to the evaluation of safety must be reported to the Sponsor by the Investigator according to the reporting requirements within the time periods specified in the protocol.

AEs determined by the Investigator to be related to study drug must be followed until resolution or until they are considered stable or for at least 30 days after discontinuation of study drug.

Any serious adverse events (SAEs) experienced after 30 days post the last dose of study drug should only be reported to the sponsor if the investigator suspects a causal relationship to the study drug.

Abnormal laboratory values or test results occurring after study enrollment constitute AEs only if they induce clinical signs or symptoms, are considered clinically significant, or require therapy.

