Subjects who are discharged from the hospital before Day 7 will have follow up contacts with study staff (phone calls or other digital media) on Days 7, 15 and 29. Early discharge subjects in the brequinar treatment group will also have samples for safety labs (hematology and chemistry) obtained either at the research facility or at an outpatient laboratory on Study Days  $7 \pm 2$  and  $15 \pm 2$ . The safety laboratory results are to be initially assessed in real time by the Principal Investigator or designated person and the Medical Monitor. Any study drug-related clinically significant out-of-range laboratories or study drug-related adverse events will be followed as needed until resolution or stable.

The in-hospital assessments and phone call visits will specifically ask about possible hematologic toxicity including any evidence of the list below. Early discharge subjects will be provided with a list of the following events in lay terms and will be instructed to call the research team if any of these events occur.

PROTOCOL NUMBER: CCB-CRISIS-01  
PROTOCOL VERSION FINAL DATE: 10SEPT2020

Page 45 of 58

- Ecchymosis/purpura/petechiae
- Epistaxis
- Hemoptysis
- Hematuria
- Gingival bleeding
- Prolonged bleeding time from needle sticks, abrasions or lacerations
- Hematemesis
- Rectal bleeding
- Blood in stool
- Any other unusual bleeding noted by the subject or caregiver

Any of these symptoms considered clinically significant will be recorded as an adverse event and must be followed until resolved or stable.

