## 15 APPENDICES

### 15.1 Appendix A: CCB-CRISIS-01 Schedule of Events

CCB-CRISIS-01 Schedule of Events	Screen	D1	D2 - D7 (± 8 hours)	Final Visit D15 (± 2 days)	F/U Phone Call 2 weeks/ Survival (± 3 days)
Procedures					
Informed Consent	X				
AE/Concomitant Medications (daily until discharge)	X	X	D1-7	X	
Medical history / History of current illness	X				
Demographics, collect Height and weight	X				
Check for Physical Exam abnormalities	X				
Pregnancy Test (urine or serum)	X				
Hematology/Chemistry	X	X (pre-dose)	D1-7	X	
Inflammatory Markers*		X (pre-dose)	D3, D5, D7	X	
DHO/brequinar PK Sample Collection & Processing		X (pre-dose)	D3, D5, D7	X (DHO only)	
Swab collection for nasopharyngeal viral load		X (pre-dose)	D3, D5, D7	X	
Clinical SARS-CoV-2 testing RT-PCR	X				
Hospital Status			D3, D5, D7	X	
NEWS2 Assessments		X	D3, D5, D7	X	
Dispense Study Medication if assigned to brequinar**		X	D2 – 5		
Drug Accountability			D7		
Survival Assessment Day 29					X

Collect information from available electronic health record (EHR), Progress Notes, and medication records; a special visit by research staff is not to be performed. Results for Hematology, Chemistry and available inflammatory markers analyzed locally are to be obtained from the EHR; do not draw another set of labs. Missed samples due to hospital staff too busy or for technical reasons unable to obtain samples will not be counted as protocol deviations. Record urinalysis results if urinalysis is clinically indicated and results are available in the EHR. Note that if the subject is discharged before Day 15, follow instructions provided in [Section 8.5](#).

Note that any visits other than Screening/Day 1 may be conducted via telephone or digital media. Missed samples/assessments when phone visits occur will not be counted as protocol deviations.

\*Inflammatory markers are to be collected from the EHR when available; otherwise process and ship samples to the central laboratory per the Laboratory Manual. DHO and brequinar samples will also be sent to the central laboratory.

\*\*If a subject in the brequinar group is discharged prior to Day 5 (has not completed taking brequinar all 5 days) the subject may be dispensed study medication to take at home on a daily basis. In this instance the subject is also to be provided with the study medication diary for drug accountability purposes.

PROTOCOL NUMBER: CCB-CRISIS-01  

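### The Day 15 adverse-event review starts at Day 7, so if an early-discharged subject's Day 7 contact does not take place, the visit procedure covers less than Section 10 requires

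*Protocol*

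**What the plan says.** All references are to the 10SEPT2020 version.

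- **Section 9.5, Final Visit Day 15:** the site is to "Review Progress Notes and the medication record to collect information for any adverse events or new concomitant medications since Day 7".
- **Synopsis, Procedures, Final Visit Day 15:** new events, changes in ongoing events, and new or "changed concomitant medications since Day 7 (collect from EHR if subject still hospitalized, otherwise by phone or other digital media").
- **Section 9.5, Days 1–7:** the review covers adverse events and "new or changed concomitant medications since previous visit", with the instruction "Repeat daily until discharge".
- **Section 10:** "All adverse events will be collected from the time of informed consent through Day 15".
- **Section 10.8:** "Subjects who are discharged from the hospital before Day 7 will have follow up contacts with study staff", on Days 7, 15 and 29.
- **Section 9.6:** "The Day 7 and 15 visits are to be conducted via telephone if the subject has been discharged from the hospital".
- **Section 9.5, Treatment:** some assessments may be lost because the subject cannot travel or the visit cannot be done remotely, and neither case counts as a deviation.
- **Section 6.1:** the primary endpoint is safety and tolerability, measured by rates of post-randomization adverse events and by safety laboratory results.

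**The concern.** The two look-back rules work differently. The Days 1–7 rule is relative: if one review is missed, the next one picks up the interval. The Day 15 rule starts at a calendar day whether or not anything was collected on that day.

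This is harmless for a subject still in hospital on Day 7, and for one who is reached on Day 7 after discharge. It matters for a subject who left earlier and was not reached. Daily review ended at discharge, and the Day 15 instruction begins after the interval in question. No section tells the site to widen the Day 15 question when Day 7 was missed. The only later scheduled contact, Day 29, is for survival status.

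The interval belongs to the primary endpoint. Section 8.1.1 requires only the first dose to be taken in hospital, so the uncovered days may include doses taken at home.

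**Working it through.** The protocol states no figure to reproduce. The check sets the passages side by side and counts days.

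**Which provision covers the time from discharge to Day 7 if the Day 7 contact fails?**

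1. Daily review (Section 9.5, Days 1–7): no, it ends at discharge.
2. Day 7 review: it would cover the interval, because it looks back to the previous visit. By assumption it did not happen.
3. Day 15 review (Section 9.5 and synopsis): no, it starts at Day 7. The synopsis adds changes in ongoing events, so an event still present after Day 7 can be picked up.
4. Section 10.8: partly. Phone visits ask about possible hematologic toxicity with no look-back limit, and early-discharged subjects are told to call about listed bleeding events. Nausea, vomiting, diarrhea, stomatitis, rash, fatigue and infection are among the commonly observed events in Section 8.2.1 and are not on that list.
5. Serious events (Section 10.5): yes, because reporting is not tied to a visit.
6. Section 10: yes as a requirement, but it sets the period to be covered, not the question to be asked at the visit.

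What remains is transient, non-serious, non-bleeding events that resolved before Day 7.

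**Length of the interval.** Let r be the day of the last completed review. The uncovered time is 7 − r days, out of 15 − 1 = 14 days from Day 1 to Day 15.

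- r = 1 (earliest discharge the text allows): 7 − 1 = 6; 6/14 = 43%.
- r = 2: 7 − 2 = 5; 5/14 = 36%. Counting only the whole days strictly between gives Days 3–6, or 4 of 15 = 27%.
- r = 5: 7 − 5 = 2; 2/14 = 14%.
- Day 7 contact completed: 0 days.

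With discharge on Day 2 after that day's dose, the interval can contain up to three home doses (Days 3, 4 and 5).

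**Weight of one subject.** With about 16 and 8 subjects per arm (Section 7.1), one subject whose only event is missed lowers that arm's rate by 1/16 = 6.25 points (brequinar) or 1/8 = 12.5 points (standard of care). This illustrates how much one subject counts. It does not estimate bias.

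**After the fix.** If the Day 15 review starts at r, the uncovered interval is 0 days whether or not Day 7 took place.

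**The case against.** The strongest reply is that Section 10 governs. It requires all events through Day 15 and says subjects will be questioned about them, and the synopsis repeats the collection window. A site that knows it missed Day 7 is still bound by that rule. This stands, and it defeats the inference that these events are never asked about. It does not remove the mismatch: a site can follow the Day 15 instruction to the letter and still fall short of Section 10.

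A second reply is that one missed call may not open the whole gap. Section 8.5 has discharged subjects return for the remaining visits where feasible, and moves visit activities to phone or digital contact where they cannot. Days 3 and 5 are scheduled assessment days, so this can be read as adding contacts on those days, each looking back to the one before. On that reading a completed Day 5 contact leaves only 2 days. The reading is open, because Section 10.8 names only Days 7, 15 and 29, and Section 8.5 stresses only Days 7 and 15.

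A reader might also infer that the protocol expects Day 7 contacts to fail. Most of the text does not say so. Section 5 excuses assessments missed because the subject cannot return to the clinic, and allows telephone visits instead. Section 9.6 directs that Day 7 be done by telephone after discharge. The note in Appendix A, "Missed samples/assessments when phone visits occur will not be counted as protocol deviations", presupposes that the call took place. Only the Treatment paragraph of Section 9.5 reaches a visit that cannot be done remotely. That is enough to show the case is foreseen and excused, but not that it is common.

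Finally, brequinar subjects have extra touchpoints in the dosing diary and the Day 7 safety laboratory sample. Neither is a general adverse-event review.

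**Conclusion.** The point holds as a narrow inconsistency that touches the primary endpoint. The Day 15 instruction covers less than Section 10 requires, and it departs from the protocol's own Days 1–7 wording. The consequence is conditional on discharge before Day 7, no completed Day 7 contact, and a site that follows the Day 15 text literally. In that case transient, non-serious, non-bleeding events between the last review and Day 7 can be under-ascertained.

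The uncovered time is at most 6 of 14 days and depends on the discharge day and on how Section 8.5 is read. Its effect on the event rate cannot be computed, because the documents give no frequency of early discharge or of missed contacts. Neither the day counts nor the per-subject percentage points should be read as expected bias. Nor do the documents show that these are the days on which drug effects are most likely: Section 8.2.1 summarises drug-related events through 21 days.

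This is a wording correction worth making because the endpoint is primary and the correction is nearly free.

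**What to change.** In Section 9.5, Final Visit Day 15, and in the matching synopsis bullet, replace the Day 7 starting point with *since the last completed adverse-event and concomitant-medication review*. Apply it to both arms. When Day 7 was completed, nothing changes. When it was not, the Day 15 review reaches back to the last time the subject was asked, and the visit instruction matches Section 10.

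The cost is one phrase in two places. No visit, call or sample is added.

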#### **Subjects in the Brequinar Treatment Group**

If the subject is in the brequinar treatment group and is being discharged prior to completing the study, ensure a hematology/chemistry sample is obtained prior to discharge on the day of discharge. The subject is to return to the research or out-patient facility for the Days 7 and 15 visits if able and permitted. If unable or not permitted to return to the research facility due to COVID-19 restrictions, the remaining visit activities except for the lab draw will be conducted by phone

PROTOCOL NUMBER: CCB-CRISIS-01  
PROTOCOL VERSION FINAL DATE: 10SEPT2020

Page 22 of 58

or other digital media. The lab draw will be performed by an outpatient laboratory at a designated facility. Lab draws for any outpatient visits for the Day 7 and 15 visits are limited to safety labs (hematology and chemistry). Additional outpatient laboratory or study visits are to be conducted as needed for follow up of adverse events including hematologic toxicities.

PROTOCOL NUMBER: CCB-CRISIS-01  
PROTOCOL VERSION FINAL DATE: 10SEPT2020

Page 23 of 58

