### **4.3 EXPLORATORY OBJECTIVES**

- To determine the change in SARS-CoV-2 nasopharyngeal viral load through Day 15
- To determine the change in inflammatory markers through Day 15
- To determine the change in dihydroorotate dehydrogenase (DHO) through Day 15
- To determine the change in brequinar concentration levels through Day 7

PROTOCOL NUMBER: CCB-CRISIS-01  
PROTOCOL VERSION FINAL DATE: 10SEPT2020

Page 24 of 58

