### **6.3 EXPLORATORY Endpoints**

- SARS-CoV-2 nasopharyngeal viral load: Day 1 (pre-dose), Days 3, 5, 7, and 15
- Inflammatory markers (to be specified in the Laboratory Manual, may include but are not limited to erythrocyte sedimentation rate (ESR), c-reactive protein (CRP), D-dimer, serum ferritin, and fibrinogen, procalcitonin, IL-6, IL-5, IL-2, IFN- $\gamma$ , final list to be determined) on Day 1 pre-dose, D3, D5, D7, D15 or at frequency per institutional standard of care. The markers are to be tested locally when possible; requested tests as listed in the Laboratory Manual that are not analyzed locally are to be shipped to the central laboratory for analysis.
- DHO concentration levels through Day 15.
- Brequinar concentration levels through Day 7

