#### 8.4.2 Study-Level Stopping Criteria

Following assessment by the Data Safety Monitoring Board (DSMB, see [Section 10.9](#)), the study is to be stopped as shown below:

- If  $\geq 4$  subjects on the brequinar treatment arm develop the same Grade 3 or 4 adverse event or symptomatic laboratory abnormality
- If  $\geq 8$  subjects on the brequinar treatment arm develop any Grade 3 or 4 adverse event or symptomatic laboratory abnormality.

### 8.5 Hospital Discharge Prior to Study Day 15

Subjects discharged from the hospital prior to the Day 15 visit are to return to a research facility when feasible for the remaining study visits. All scheduled study assessments are to be completed at these visits when conducted at a research facility.

PROTOCOL NUMBER: CCB-CRISIS-01  
PROTOCOL VERSION FINAL DATE: 10SEPT2020

Page 30 of 58

For subjects in the brequinar treatment group discharged from the hospital prior to Day 5, the subject is to take home the remaining doses of brequinar for daily self-administration. All subjects (brequinar and SOC) should have the scheduled assessments, e.g. lab samples and the nasopharyngeal swab, on the day of discharge and enter these results on the appropriate EDC page. Following discharge, subjects are to return to the research or out-patient lab collection facility for the remaining study visits, if feasible. Out-patient lab results are to be entered into the EDC and reviewed by a member of the study team. It is important that every effort be made to have subjects return at least on Days 7 and 15, if feasible. Subjects in the brequinar group are to record brequinar dosing on the medication diary provided by the study team. The study team will arrange for the subject to return any unused study medication to the research facility.

For all subjects, if discharge occurs on Days 10, 11, or 12, ensure a hematology/chemistry sample has been obtained on the day of discharge and record these results on the appropriate EDC page. Following discharge, the subject is to return to the research or out-patient lab collection facility for the Day 15 visit, if feasible. Out-patient lab results are to be entered into the EDC and reviewed by a member of the study team.

If discharge occurs on Days 13, 14 or 15, complete the Day 15 Final Visit activities prior to discharge. No further visits are required unless follow up is needed for a study drug-related AE or an SAE; the Day 29 mortality assessment is still to take place.

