### **11.3 Efficacy Analyses**

Efficacy will be assessed in terms of mortality, hospitalization status and duration, NEWS2 score, viral load (plasma and nasopharyngeal), and inflammatory markers.

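### Contradictory instructions on sampling discharged subjects for the exploratory Day 15 viral load, inflammatory marker and DHO objectives

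*Protocol*

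**What the plan says.** All references are to the current protocol version, dated 10 September 2020.

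**What is to be measured.** Section 4.3 sets these exploratory objectives: "To determine the change in SARS-CoV-2 nasopharyngeal viral load through Day 15" and "To determine the change in inflammatory markers through Day 15". Section 6.3 adds "DHO concentration levels through Day 15". Section 9.4 and Appendix A put the swab, the inflammatory markers and the DHO sample on Days 1, 3, 5, 7 and 15.

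**Text that samples discharged subjects.** Section 8.5 and the matching synopsis text ask discharged subjects of both arms to come back to a research facility where feasible, and add: "All scheduled study assessments are to be completed at these visits when conducted at a research facility". They stress Days 7 and 15 in particular. The synopsis lists the Day 15 DHO and cytokine samples with no condition on hospital status.

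**Text that does not.** For Day 15, Section 9.5 says to "collect samples for DHO and cytokine panel to be analyzed at the central laboratory if subject still hospitalized". Section 9.6 says: "The Day 7 and 15 visits are to be conducted via telephone if the subject has been discharged from the hospital". That sentence goes on to mention lab draws for the brequinar group only. Section 3.9, under its brequinar-group heading, says: "Lab draws for any outpatient visits for the Day 7 and 15 visits are limited to safety labs (hematology and chemistry)".

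**A related mismatch.** Section 11.3 lists among the efficacy measures "viral load (plasma and nasopharyngeal), and inflammatory markers". Sections 4.3, 6.3, 9.4 and 9.5 and Appendix A schedule a nasopharyngeal swab but no plasma virology sample.

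**The concern.** Recovery leads to discharge. If discharge also ends sampling, the late values describe people selected by not having recovered, and a Day 15 summary by arm compares two such selected groups. The selection could differ between arms in two ways: brequinar may change who goes home, and Section 9.6 names post-discharge draws for one arm only.

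The study title refers to an anti-coronavirus response, and these exploratory measures are where that response and the drug's effect on its target would be described. Appendix A states that samples missed because a visit was by telephone are not protocol deviations, so deviation reporting would not reveal the loss. Two sites could act differently, each in line with some part of the protocol.

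**Working it through.** **1. The same subject under each section.** Take a subject discharged before Day 15 who is able to attend a research facility.

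| Source | Day 15 swab | Day 15 DHO and cytokines | Arms |
|---|---|---|---|
| 8.5 and synopsis | taken | taken | both |
| 9.4 and Appendix A | scheduled | scheduled | both |
| 9.5, Day 15 list | taken, no condition | not taken | both |
| 9.6 | not possible by telephone | not possible by telephone | draws named for brequinar only |
| 3.9 | not addressed | excluded, if an outpatient visit includes a research-facility visit | brequinar heading |

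A site cannot satisfy every row. The hospitalization condition in 9.5 attaches only to the Day 15 DHO and cytokine samples. The Day 15 swab and the Day 3, 5 and 7 samples in 9.5 carry no such condition; after discharge, the swab and the Day 7 samples are at risk only through the telephone instruction in 9.6 or an outpatient-laboratory visit.

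**2. Plan's own figure.** About 24 subjects at 1:2 gives 24/3 = 8 SOC and 2 × 24/3 = 16 brequinar, matching Section 7.1. The protocol states no power or alpha for these endpoints.

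**3. Illustration if 9.5 and 9.6 are followed.** Let d be the fraction discharged by Day 15. It is not in the protocol; the entry criteria require only an expected stay of at least 24 hours. Expected Day 15 DHO and cytokine samples are n × (1 − d), all from inpatients whatever d is. The chance that the SOC arm has at most one sample is d^8 + 8(1 − d)d^7.

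| d (assumed) | SOC, of 8 | Brequinar, of 16 | P(SOC has 0 or 1) |
|---|---|---|---|
| 50% | 4.0 | 8.0 | 3.5% |
| 70% | 2.4 | 4.8 | 25.5% |
| 90% | 0.8 | 1.6 | 81.3% |

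**4. Illustration if 8.5 is followed.** Let r be the fraction of discharged subjects who return to a research facility, also not in the protocol. The inpatient share of Day 15 samples is (1 − d)/((1 − d) + d·r).

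| d (assumed) | r = 25% | r = 50% | r = 75% | r = 100% |
|---|---|---|---|---|
| 50% | 80% | 67% | 57% | 50% |
| 70% | 63% | 46% | 36% | 30% |

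Inpatients are the majority only when r is below (1 − d)/d; at d = 70% that is 0.3/0.7 = 43%.

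The gap between steps 3 and 4 shows what the choice of governing section could decide. It is not an estimate of what will happen.

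**The case against.** The strongest reply is that Section 8.5 governs. Section 9.5 refers to it twice for discharged subjects, and Appendix A does so as well. On that reading the condition in 9.5 is a slip and both arms are sampled on return. This carries weight, and it is why the point is a contradiction and not a uniform restriction. It does not remove the problem: 9.6 also cites 8.5 and still orders telephone visits, and the Day 15 list in 9.5 gives site staff a plain instruction not to take the DHO and cytokine samples.

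Section 3.9 has an innocent reading. It first sends the subject back, then offers an outpatient laboratory to those who cannot return, then limits outpatient draws to safety labs. Read in that order, the limit describes the fallback and agrees with 8.5. The sentence is ambiguous, not clearly wrong.

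Some loss after discharge is a deliberate allowance for COVID-19 travel limits, and no rewording recovers a subject who cannot come back. That stands.

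The endpoints are exploratory and all analyses are descriptive. Dosing ends on Day 5, so samples on Days 3, 5 and 7 cover the treatment window. A reader might infer that the trial could not show faster viral clearance; the unconditional swabs on those days do not support so broad a claim.

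On plasma viral load, samples may be banked and the Laboratory Manual is not shown. To say that the measure can never be produced would go too far. What holds is that 11.3 names it and the protocol schedules no sample for it.

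**Conclusion.** The point holds as an internal contradiction. Sections 9.5 and 9.6 conflict with 8.5, the synopsis, 9.4 and Appendix A on whether discharged subjects are sampled, and 3.9 can be read either way. Where a site follows 9.5 and 9.6, Day 15 DHO and cytokine data come only from inpatients, and the swab is lost wherever the visit is by telephone. Missingness then depends on recovery and possibly on arm.

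Its size cannot be computed from the protocol; the tables above rest on assumed discharge and return rates. A reader might infer that the late data will come mainly from subjects who did not recover. That is certain only for Day 15 DHO and cytokines at sites that follow 9.5 and 9.6. Under 8.5 it depends on how many return, and it does not extend to the whole Day 1 to Day 15 series.

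The primary endpoint rests on adverse events and hematology/chemistry, not on these samples, so this route does not affect it. The correction is still worth making, because it costs little and protects the only data on antiviral and pharmacodynamic response.

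**What to change.** - **Section 9.5, Day 15:** delete the condition that ties the DHO and cytokine samples to still being in hospital.
- **Sections 9.6 and 3.9:** reword to match 8.5. Discharged subjects in both arms who attend a research facility have all scheduled samples: swab, DHO, cytokines and safety labs. A telephone visit, or safety labs at an outpatient laboratory, is the fallback only for those who cannot attend.
- **Section 11.3:** strike plasma viral load, since no plasma virology sample is scheduled.

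The cost is amendment wording and a few more samples to process, all already on the Appendix A schedule. An extra swab and tube at every discharge from Day 2 to Day 12 is not needed: it would add samples on days that Appendix A does not list, and resolving the contradiction does not require it.
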